5.2.1 Procedures for randomisation

A randomisation list will be prepared using a validated computer program (GRand). Patients will be randomised to treatment with either tralokinumab or placebo in a ratio of 1:1.

Randomisation to IP will be done via an IVRS/IWRS at Visit 2. The IVRS/IWRS will sequentially allocate the treatment and provide the randomisation number and the appropriate kit ID from those available at the study site. The randomisation is carried out at the study level and the assigned randomisation numbers and the associated kit IDs will not be sequential within a study site. Forced randomisation is not allowed.

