12.2.1 Analysis of primary variable

The primary variable, clinical response at week 8, will be analyzed using a one-sided Cochran-Mantel-Haenszel (CMH) chi-square test, with glucocorticosteroid-refractory status as a stratification factor. The null hypothesis that the proportion of patients responding on tralokinumab is less than or equal to the proportion of patients responding on placebo will be rejected in favour of the alternative hypothesis, that the proportion of patients responding is higher on tralokinumab than on placebo, if the one-sided p-value is <0.05 .

The number and proportion of patients responding in each treatment arm will be displayed. The difference in proportions between tralokinumab and placebo will be presented using point estimate and 95% confidence intervals.

A sensitivity analysis will be performed, where patients with biopsies from affected mucosa where the central pathology assessment reported normal histology at baseline, will be excluded.

To assess the impact of premature discontinuations from IP on the primary variable, time to discontinuation of IP may be analysed using Kaplan-Mayer curves. The time to discontinuation of IP will be calculated as the date of IP discontinuation minus the date of randomization +1 day.

In addition, clinical response at week 8 will be summarized descriptively based on the following grouping variables: glucocorticosteroid-refractory status (yes or no), time since first diagnosis (≤ 5 years or > 5 years), prior immunomodulatory therapy (yes or no), and affected area in colon (rectosigmoideum involvement only, left side involvement only or extensive involvement).

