12.2.2 Analysis of secondary efficacy variables

12.2.2.1 Mucosal healing and clinical remission at week 8

Proportion of patients with mucosal healing and proportion of patients in clinical remission, will be analyzed and presented in the same way as the primary variable, except that no subgroup analyses will be performed.

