12.2.2.2 Change from baseline in Mayo score

Depending on the distribution of the data, change from baseline to week 8 in Mayo score will be analyzed using either ANCOVA or cumulative logit methodology. Mayo score at baseline will be included as a covariate, and treatment and glucocorticosteroid-refractory status as factors in the model. Patients with no week 8 assessment and from which change from baseline cannot be calculated, will be excluded from the analysis.

Changes from baseline to all scheduled assessments in each individual subscore will be presented in shift tables.

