12.2.2.3 Change from baseline in partial Mayo score

Repeated measures analysis will be used to analyze the change from baseline in partial Mayo score. The model will include treatment, glucocorticosteroid-refractory status, partial Mayo score at baseline, visit, and treatment by visit interaction as explanatory variables. The contrasts of interest are the differences at each visit between tralokinumab and placebo. Depending on the distribution of the data, partial Mayo score will be treated as either a continuous or as an ordered categorical variable.

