12.2.2.4 Markers of disease activity (CRP, calprotectin) and intestinal leakiness (albumin)

Repeated measures analysis will be used to analyze the change from baseline in markers of disease activity and intestinal leakiness. The model will include treatment, baseline value, visit, and treatment by visit interaction as explanatory variables. The contrasts of interest are the differences at each visit between tralokinumab and placebo.

Markers of disease activity and intestinal leakiness will be log-transformed before analysis, unless otherwise is stated in the SAP. The number of CRP values below limit of quantification will be assessed before analysis to ensure the model appropriateness. In case of large number of values below limit of quantification another method of analysis should be considered for CRP, this method will be stated in the SAP.

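### Randomisation is not stratified by glucocorticosteroid-refractory status, the factor that stratifies the primary test: a minor gap that is cheap to close before the first patient

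*Protocol*

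**What the plan says.** Protocol section 5.2.1 is the only place that describes allocation. It says "Patients will be randomised to treatment with either tralokinumab or placebo in a ratio of 1:1", that "The IVRS/IWRS will sequentially allocate the treatment and provide the randomisation number", and that "The randomisation is carried out at the study level". No stratification factor is named there or elsewhere in the protocol for randomisation. The word in the synopsis's statistical methods refers to the test, not to the list.

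The analysis sections rely on one baseline factor throughout the Mayo-based endpoints:

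- Section 12.2.1, clinical response: a one-sided CMH test "with glucocorticosteroid-refractory status as a stratification factor". The same factor is the first of the descriptive subgroups.
- Section 12.2.2.1, mucosal healing and remission: these "will be analyzed and presented in the same way as the primary variable, except that no subgroup analyses will be performed".
- Section 12.2.2.2, change in Mayo score: "Mayo score at baseline will be included as a covariate, and treatment and glucocorticosteroid-refractory status as factors in the model".
- Section 12.2.2.3, partial Mayo score: "The model will include treatment, glucocorticosteroid-refractory status, partial Mayo score at baseline, visit, and treatment by visit interaction as explanatory variables".

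Section 12.2.1 also promises the responder proportions by arm and their difference with a 95% confidence interval. It does not say whether that difference is stratified.

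**The concern.** The sponsor has picked one prognostic factor as important enough to condition the primary test on, and randomises through a central system that could balance it, but does not ask the system to do so. The p-value is protected against an uneven split because the CMH test compares arms within strata. The raw arm proportions shown beside it are not, and the difference in proportions is protected only if it is computed by stratum.

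A second, smaller matter is timing. The protocol does not define glucocorticosteroid-refractory and does not say when a patient's stratum is recorded. A randomisation stratum would force both to be settled before allocation. The SAP cannot supply this: section 12.2 requires it only before clean file, and by then allocation is complete.

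**Working it through.** **Inputs from the protocol (12.3, 5.2.1).** Response 65% v 35%, one-sided alpha 0.05, power 90%, 53 per arm, 110 randomised 1:1 (taken as 55 per arm).

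**Assumed inputs.** Share of refractory patients 15-40%, that is K = 16 to 44 of 110. Response gap between refractory and non-refractory patients 20-30 points. The protocol gives neither.

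**1. The plan's own figure.** Pooled two-proportion formula: n = [1.645·√(2·0.5·0.5) + 1.282·√(0.65·0.35 + 0.35·0.65)]² / 0.30² = (1.163 + 0.864)² / 0.09 ≈ 45.7. With the continuity correction: (45.7/4)·[1 + √(1 + 4/(45.7·0.30))]² ≈ 52.1, rounded up to 53. The stated 53 per arm is reproduced, and nothing in this point changes it.

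**2. Chance imbalance.** With 55 per arm, the number X of refractory patients in one arm is hypergeometric (110, K, 55). The difference in refractory share is |2X − K|/55, with SD (2/55)·√[55·(K/110)·(1 − K/110)·(55/109)].

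| K (share) | SD, points | P(≥10 points) | P(≥15 points) |
|---|---|---|---|
| 16 (15%) | 6.8 | 0.175 | 0.013 |
| 17 (15%) | 6.9 | 0.112 | 0.033 |
| 22 (20%) | 7.7 | 0.233 | 0.030 |
| 33 (30%) | 8.8 | 0.212 | 0.095 |
| 44 (40%) | 9.4 | 0.331 | 0.079 |

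The probabilities are jagged because counts are whole numbers: for even K the first difference past 10 points is 6/55 = 10.9, for odd K it is 7/55 = 12.7. Over every K from 16 to 44, P(≥10 points) runs from 0.11 to 0.33.

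**3. Effect on an unstratified comparison.** Shift = imbalance × response gap. For 10 points: 10 × 0.20 = 2 points, 10 × 0.30 = 3 points. For 15 points: 3 to 4.5 points. The planned effect is 65 − 35 = 30 points.

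**4. Effect on the CMH test.** The information kept, relative to perfect balance, is Σ n₁n₀/n over the strata divided by 55·55/110 = 27.5. Example with K = 22 split 14 v 8 (a 10.9-point imbalance): 14·8/22 + 41·47/88 = 5.09 + 21.90 = 26.99, and 26.99/27.5 = 98.1%. Averaged over all splits it is 99.1%, whatever the prevalence.

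**5. Simulation of the one-sided CMH test.** 53 per arm, 200,000 runs per setting, refractory share 10-50%, gap 20 or 30 points, no continuity correction.

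| | Unstratified list | Stratified list |
|---|---|---|
| Power | 93.5-95.1% | 93.7-95.2% |
| Type I error | 0.050-0.051 | 0.049-0.051 |

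The largest gain in any one setting is about 0.3 points of power.

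**The case against.** The strongest reply is that nothing here is wrong. Adjusting for a prespecified baseline factor that was not a randomisation stratum is legitimate, and in a 110-patient phase IIa trial a plain list is a defensible choice. The imbalance probabilities count uneven splits, not harm to the primary test, and steps 4 and 5 show that the test barely notices them. All of this stands, and it sets the severity at minor.

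A reader might infer more than the protocol supports:

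- **That the primary test is biased or underpowered.** It is neither. Type I error holds and power is essentially the same under both lists.
- **That stratifying would make the refractory subgroup table informative.** That table is descriptive only. At 16-22 refractory patients, an even split still gives just 8-11 per arm.
- **That the stratum is assigned only later, from case report form data.** The protocol does not say so. Medical history and disease characteristics are collected at Visit 1, and the treatment codes stay closed until evaluability decisions are documented (5.4.2). The protocol is merely silent on when refractory status is classified.
- **That the biomarker model in 12.2.2.4 must gain the factor so that all efficacy analyses carry it.** That model ("The model will include treatment, baseline value, visit, and treatment by visit interaction as explanatory variables") omits it, but the modified Riley test in 12.2.2.5 does too, being stratified by baseline score alone. Adding the factor to 12.2.2.4 is optional and separate from this point.

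One caveat applies to the reading itself. Section 5.2.1 does not use the word unstratified; that is read from the study-level list and the absence of any factor.

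What the reply leaves untouched is the displayed proportions, the unspecified form of their difference, and the lack of a stratum fixed before allocation.

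**Conclusion.** The point holds as a minor, cheap improvement. The primary analysis is valid as planned and the sample size is unaffected. The exposure is a chance of about 11-33% that the arms differ by 10 points or more in the one factor the plan conditions on. A 10-point imbalance moves the raw arm comparison by 2-3 points against a planned 30, and moves the reported difference equally if that is not stratified. These sizes rest on an assumed 15-40% prevalence and an assumed 20-30 point response gap, with arms of 55.

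**What to change.** - **5.2.1:** stratify the central list by glucocorticosteroid-refractory status (yes/no), with the status defined in the protocol and entered in the IVRS/IWRS at Visit 2 before allocation.
- **12.2.1:** use that recorded stratum in the CMH test, and state that the difference in proportions and its confidence interval are stratified by the same factor.

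The cost is one IVRS/IWRS question and two lists instead of one, in a system already planned. Occasional stratum entry errors will occur; analyse the stratum as randomised. The list change must be made before the first patient is randomised. If the sponsor prefers a plain list, 5.2.1 should say that this is deliberate, and the definition, its recording before allocation and the stratified difference should still be adopted.

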5.3 Procedures for handling patients incorrectly enrolled or randomised

Patients who fail to meet the inclusion/exclusion criteria should not, under any circumstances, be enrolled or receive study medication. There can be no exceptions to this rule.

Where patients that do not meet the inclusion and/or exclusion criteria are enrolled in error, or incorrectly started on treatment, or where patients subsequently fail to meet the restrictions

during the study (see section 5.1), the investigator should inform the Study Physician immediately. The Study Physician is to ensure all such contacts and subsequent decisions are appropriately documented.

5.4 Blinding and procedures for unblinding the study

5.4.1 Methods for ensuring blinding

The study will be conducted in a double blind fashion. Tralokinumab and placebo are visually distinct from one another. Tralokinumab appears to be slightly opalescent, whereas placebo appears to be a clear solution. There is also a difference in viscosity between the active and placebo IP. Active IP has a viscosity of approximately 13 centipoise (cP), whereas placebo IP has a viscosity of approximately 1 cP.

The sponsor staff, the patients, and the investigators involved in the treatment of patients or in the clinical evaluation of patients will not be aware of the treatment received (International Conference on Harmonisation [ICH] E9).

IP will be handled by an unblinded IP manager/pharmacist at the study site and will be administered by an unblinded study staff member who will not be involved in the management or evaluation of study patients. Handling and administration of IP could be delegated the same study staff member.

The staff responsible for the dose preparation and administration of IP must have appropriate training in the subcutaneous administration of drugs.

An unblinded Site Monitor will be unblinded to perform IP accountability.

5.4.2 Methods for unblinding the study

During the whole study period no member of the blinded study team at AstraZeneca, at MedImmune or at the investigational sites or any Contract Research Organization handling data will have access to the randomisation scheme. Exception from this rule are relevant persons at MedImmune Clinical Research Pharmacy Services (CRPS) or their designee, where the information is needed to package study medication, and the Patient Safety departments at MedImmune and AstraZeneca.

Individual treatment codes, indicating the treatment randomisation for each randomised patient, will be available to IP manager or pharmacists from the IVRS/IWRS. Routines for this will be described in the IVRS/IWRS manual that will be provided to each study site.

The treatment code should not be broken except in medical emergencies when the appropriate management of the patient requires knowledge of the treatment randomisation. The investigator documents and reports the action to AstraZeneca, without revealing the treatment given to patient to the AstraZeneca staff. Instructions for unblinding an individual patient's IP are contained in the IVRS/IWRS manual.

In the event that the treatment allocation for a patient becomes known to the investigator or other study staff involved in the management of the patients, or needs to be known to be able

to treat the patient for an AE, the sponsor must be notified immediately by the investigator and preferably, before unblinding.

AstraZeneca retains the right to break the code for SAEs that are unexpected and are suspected to be causally related to an IP and that potentially require expedited reporting to regulatory authorities. Treatment codes will not be broken for the planned analyses of data until all decisions on the evaluability of the data from each individual subject have been made and documented.

5.5 Treatments

5.5.1 Identity of investigational products

Table 3 Identity of IPs

IP	Dosage form and strength	Manufacturer
Tralokinumab (CAT-354)	300mg Formulated at a nominal concentration of 150mg/mL in [REDACTED] [REDACTED] See Table 4 for full list of excipients.	MedImmune
Placebo	Placebo contains the same excipients, in the same concentration only lacking tralokinumab	MedImmune

Table 4 Tralokinumab (CAT-354) composition

Ingredient	Concentration	Unit Formula per 150 mg Vial (nominal)
Active Ingredient		
CAT-354	150mg/mL	150mg
Other Ingredients		
[REDACTED]	[REDACTED]	[REDACTED]
[REDACTED]	[REDACTED]	[REDACTED]
[REDACTED]	[REDACTED]	[REDACTED]
[REDACTED]	[REDACTED]	[REDACTED]
[REDACTED]	[REDACTED]	[REDACTED]

The IP (tralokinumab and placebo) is filled into 3ml glass vials, stoppered, and sealed with an aluminium overseal.

IP will be supplied to the site as kits containing one vial per kit. Each kit has a unique number that is identical to the printed number on the vial label within the kit.

Materials Safety Data Sheets will be provided detailing procedures required for the safe handling of the IP.

5.5.2 Doses and treatment regimens

Patients will receive either:

- Tralokinumab (CAT-354) 300mg will be administered during study visits as 2 (two) sc 150mg injections every 2 weeks for 12 weeks starting from Visit 2 (week 0),
- Placebo will be administered during study visits as 2 (two) sc injections every 2 weeks for 12 weeks starting from Visit 2 (week 0).

Sites will be supplied also with needles and syringes required for IP administration. **Do not use any other materials other than those provided by the MedImmune.**

More details regarding handling of drug supplies and accountability for the IP will be provided separately.

Any defects with the IP must be reported immediately to the MedImmune Product Complaint Department (see [Table 5](#)) by the unblinded IP Manager/pharmacist and further notification to the unblinded Site Monitor. All defects will be communicated to MedImmune and investigated further with the Product Complaint department. During the investigation of the product complaint, all IP must be stored at labelled conditions unless instructed otherwise.

Defects may be related to component, product, and packaging and labelling issues. The table below includes, but is not limited to, descriptions of product complaints that should be reported.

Table 5 Complaint Categories Descriptions

Complaint Category	Brief Description
Component Issue	Defect in container or dosing mechanism of IP. The component defect may be damaged, missing or broken. Component examples include vials, stoppers and caps.
Product Issue	Defect in the product itself. The product appearance has visual imperfections such as foreign particles, crystallization, discoloration, turbidity, insufficient volume or anything that does not apply to the product description.
Packaging/Labelling Issue	Defect in the packaging or labelling of the product. The packaging or labelling defects may be damaged, unreadable, or missing label.

When reporting a product complaint, be prepared to provide the following information:

- Customer Information (reporter name, address, contact number, date of complaint),
- Product Information (product name, packaging kit number or lot number, expiry date, clinical protocol number),
- Complaint Information (complaint category, description).

Table 6 Product Complaint Department Contact Information

Email	
Phone	
Fax	
Mail	MedImmune, LLC

5.5.2.1 Dose Preparation

The IP should be equilibrated for a minimum of 30 minutes/maximum of 1 hour to room temperature then swirled GENTLY 5-10 times to mix prior to use.

The IP Vials MUST NOT be inverted during swirling.

The dose of IP for administration must be prepared using an aseptic technique by the unblinded pharmacist/unblinded study site staff as follows:

1. The IP is viscous therefore it should be confirmed that all the contents are at the bottom of the vial before attempting to withdraw liquid from the vial. The vial may require gentle tapping on the side to dislodge any liquid that may be held in the stopper recess.
2. The IP should be withdrawn (slowly) from the vial into the 1 ml hypodermic syringe, using a 19G x 1½ inch hypodermic needle.

When withdrawing the IP, the vial should be tilted at an angle to ensure that 1mL can be extracted.

3. Syringe should be inverted and tapped to remove all air bubbles.
4. The 19G needle will be changed to the 27G x ½ inch hypodermic needle. New needle will be capped until administration.

The syringe must be prepared immediately for administration so that it does not require any further labelling but maintains the blind.

5.5.2.2 Treatment Administration

The first day of dosing is considered Day 1 (Week 0). IP (tralokinumab or placebo) must be administered during study visit, the same day the IP is assigned. If there is a delay in the administration of IP such that it will not be administered within the specified timeframe, the study monitor must be notified *immediately*.

The IP will be administered by 2 sc injections. An unblinded qualified study staff member, who will not be involved in the management of the patients, will inject the IP into the sc tissue of the anterior thigh or abdomen.

Two injections (150mg per injection) are required in order to administer tralokinumab at the required dose of 300mg. Therefore at each administration (tralokinumab or placebo) 2 separate injection sites on the anterior thigh or abdomen at least 3cm apart should be used. Injection sites should be rotated at each visit.

The IP will be administered via a 27-gauge syringe. The person administering the dose will wipe the skin surface of the anterior thigh or abdomen with alcohol and allow to air dry. The skin will be pinched to isolate the sc tissue from the muscle. The needle will be inserted at a 90-degree angle approximately halfway into the sc tissue. The IP will be slowly injected (at least 5-second duration is recommended) into the sc tissue using gentle pressure. The area should not be massaged after injection.

5.5.2.3 Monitoring of Dose Administration

Vital signs (blood pressure, temperature, and pulse rate) will be obtained before IP administration on all treatment visits. After IP administration, patients will be monitored for immediate drug reactions; vital signs will be taken immediately after administration of IP and at least every 30 minutes thereafter. For the first 4 doses of IP, patients will remain at site for a minimum of 2 hours or until stable, whichever is later. For the 5th, 6th, and 7th doses of IP, patients will remain at site for a minimum of 1 hour or until stable, whichever is later. The investigator will determine if and when a patient can be discharged from the study site.

As with any antibody, allergic reactions to administration of tralokinumab are possible. The World Health Organization has categorized anaphylaxis into 2 subgroups, which are clinically indistinguishable: immunologic (IgE-mediated and non-IgE-mediated [eg, IgG and immune complex mediated]) and nonimmunologic ([Johansson et al 2004](#)).

The clinical criteria for defining anaphylaxis for this study are listed in Appendix F, together with a guide to the signs and symptoms and management of acute anaphylaxis. Appropriate drugs, such as epinephrine, antihistamines, glucocorticosteroids etc, and medical equipment to treat anaphylactic reactions must be immediately available at study sites, and study staff should be trained to recognize and treat anaphylaxis according to local guidelines.

If an anaphylactic reaction occurs (see Appendix F), a blood sample will be drawn from the patient as soon as possible after the event, at 60 minutes \pm 30 minutes after the event, and at discharge for analysis of serum tryptase.

